**Methods:**

Objective determination of levels of physical activity, sedentary lifestyle and sleep quality: accelerometry

The accelerometer used was the Actigraph wGT3X-BT, which is a small and light triaxial accelerometer (4.6 x 3.3 x 1.5 cm, 19 g) with a response frequency of 30 to 100 hertz. This device was used to measure different objective parameters such as physical activity and its intensity, energy expenditure, metabolic equivalents rhythms (MET), weekly steps, sedentary bouts and sleep latency and efficiency. Participants wore the accelerometer held with an elastic band on the non-dominant wrist for 7 consecutive days and without interruption, except for those times of the day in which the correct operation of the device could be compromised (showers or any activity related to water). Subsequently, the files generated by the accelerometer were analyzed through a specific software called Actilife 6 (Actigraph, Pensacola, USA).

Determination of perceived levels of general health, stress, anxiety, fatigue, depression and sleep quality: questionnaires

Participants had to fill out a series of validated questionnaires to identify possible subjective health and mental states.

SF-36 Questionnaire. This is an instrument that provides results about the health status of a general population covering 8 scales: physical function, physical role, body pain, general health, vitality, social role, emotional role and mental health. The scales are ordered so that the higher the score, the better the health status (0 to 100).

Sleep Quality in Healthy Lifestyle and Personal Control Questionnaire (HLPCQ). The HLPCQ is a questionnaire whose main objective is to detect and quantify lifestyle patterns that reflect health empowerment, as evidenced by the levels of stress and of the internal locus of control. It also includes a section with various questions to measure sleep quality where higher scores indicate better sleep quality.

The State-Trait Anxiety Inventory (STAI). This questionnaire analyzes the degree of anxiety that each participant shows. It is divided into two parts: trait-anxiety (what they usually or generally felt) and state-anxiety (their expressed emotions at a specific moment), in which higher scores indicate a higher state of anxiety.

The Perceived Stress Scale (PSS). This questionnaire allowed the frequency at which individuals had experienced certain stressful feelings to be assessed, as well as their thoughts in the last month.

Brief Fatigue Inventory (BFI). Brief screening tool designed to assess the severity and impact of fatigue on daily functioning. The higher the score, the higher the degree of fatigue.

Beck's Depression Inventory (BDI). This questionnaire was used to find out how the participants had felt during the last week, including the day of the test, with which it was possible to determine whether or not they presented signs of depression. Higher scores indicated higher signs of depression.

#### Blood and saliva sampling

Blood samples were collected from the subjects at 8 am and were deposited into collection tubes containing anticoagulant EDTA and coagulating agents to isolate plasma and serum, respectively. The plasma and serum were centrifuged, respectively, at 1.600 and 1800 x g for 10 minutes. Serum and plasma samples were coded and re-frigerated gradually at -20°C as they were obtained. Finally, samples were stored at -80°C until further analysis.

Saliva samples were obtained using a non-invasive method (Collection methods saliva Bio Oral swab, Salimetrics). Participants were asked not to ingest any type of food or drink with sugars, alcohol and/or caffeine, as well as tobacco, at least 12 hours prior to the tests. Volunteers were asked to open the packaging and remove the sterile swab for proper placement in the mouth under the tongue and were recommended to hold it for at least 2 minutes, to ensure against fluctuations in the volume of the sample. Immediately after, samples were refrigerated at -20°C and finally stored at -80°C until further analysis.

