**Design:**

This investigation was a triple blinded, randomized, placebo-controlled pilot study designed to identify the possible differing effects of the synbiotic Gasteel Plus® supplementation between sedentary individuals and soccer players. Subjects were asked to maintain their regular lifestyle and the participants were prohibited from consuming probiotics, prebiotics or fermented products (yogurt or other foods) to avoid unnecessary interference during the experimental periods. Presenting injury or illness would result in exclusion from the study. All participants were also asked to provide written informed consent before participating in the study, which had been previously approved by the ethics committee of the Catholic University of Murcia (Spain) following current legislation (CE031810).

On two separate days, the "baseline-tests" and "final-tests" were conducted. All participants performed a series of tests, before which they had to fast. The order and schedule (8 am) of the tests was the same for the "final-test" and the same materials and procedures were used. A period of 30 consecutive days elapsed between the base-line and final tests, during which the participants had to ingest their supplement (synbiotic or placebo). Accelerometers were distributed one week prior to the baseline test and the week after the final test. Blood and saliva sampling were taken early in the morning and questionnaires were filled out on the two testing days. The treatment was carried out during the last fortnight of May 2019 and the first fortnight of June of the same year, coinciding with situations of possible physical and mental stress in both participant groups, being at the end of an examination period, as well as the end of the soccer season.

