### Determination of immuno-neuroendocrine parameters

For the determination of the pro-inflammatory and anti-inflammatory cytokines studied (IL-1 $\beta$  and IL-10), an instrument based on flow cytometry was used: the Lu-minexTM 200 System instrument (Luminex Corporation, Texas, USA) using the Pro-cartaPlex TM Multiplex Immunoassay. Catecholamines such as dopamine, epinephrine and norepinephrine and also stress hormones like serotonin, cortisol, corticotropin-releasing hormone (CRH) and the adrenocorticotropic hormone (ACTH) were analyzed by competitive inhibition enzyme immunoassays (ELISA), using respectively: Dopamine Research Immunoassay, General Epinephrine (EPI) RD-EPI-Ge-96T and General Noradrenaline (NE) RD-NE-Ge-96T, General 5-Hydroxytryptamine (5-HT) RD-5-HT-Ge, The DetectX Cortisol Immunoassay Kit, Human Corticotropin Releasing Hormone (CRH) RD-CRH-Hu (Kelowna, BC, V1W 4V3, Canada) and Human ACTH (Adrenocorticotropic Hormone) ELISA Kit (Elabscience, USA). To determine immuno-globulin A in saliva, samples were analyzed by indirect enzyme immunoassay kit through the Salivary Secretory IgA Kit (Salimetrics LLC, USA). The procedures followed the instructions of the manufacturers, and the findings were measured using an ELISA auto analyzer to quantify color intensity (Sunrise, Tecan, Männendorf, Switzerland).

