It should be noted that both groups presented healthy baseline levels of the inflammatory and immune parameters analysed. No significant differences in the IL-1 $\beta$  concentrations were observed between the sedentary and athlete groups. However, a different behaviour ( $p<0.05$ ) between the two groups was found in response to the synbiotic intervention: while the synbiotic increased ( $p<0.05$ ) the systemic concentration of IL-1 $\beta$  in the sedentary group, it slightly decreased in the soccer player group.

No significant variations (except a potential placebo effect in the sedentary group) were found in the IL-10 concentration. There were also no significant differences in the levels of immunoglobulin A between groups, or as a consequence of the intervention.

A lower concentration without significant differences were found in the dopamine concentration of the soccer players group. However, training affected the response to the synbiotic intervention ( $p<0.05$ ), since it induced a significant increase ( $p<0.05$ ) in the dopamine concentration only in the athletes. This effect cannot be attributable to a potential placebo effect of the intervention. However, the decrease ( $p<0.05$ ) in epinephrine levels in the sedentary group administered with the synbiotic compared to their basal levels could potentially be attributed to a placebo effect of the intervention. In addition, there were also no significant changes in norepinephrine. Basal concentration of serotonin was, however, higher ( $p<0.05$ ) in the athlete group than in the sedentary group, but statistical differences with the synbiotic intervention were not observed.

Finally, the results corresponding to CRH showed a lower systemic concentration of CRH than sedentary volunteers. In addition, the behaviour of CRH secretion in response to the synbiotic intervention was also different ( $p<0.05$ ) between the athlete group and the sedentary group, decreasing significantly ( $p<0.05$ ) in the sedentary group with respect to their baseline levels (as also found with the placebo) and increasing slightly in the athlete group. The latter cannot be attributable to a placebo effect of the intervention. There were no significant differences in levels of cortisol and ACTH between groups or as a consequence of the intervention.

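### No rest or posture is described before the stress-hormone blood draws, so within-arm falls and the athlete–sedentary CRH difference cannot be read as supplement effects

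*Combined protocol and SAP*

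**What the plan says.** The section on blood and saliva sampling fixes the hour: "Blood samples were collected from the subjects at 8 am". It then covers tubes, centrifugation and storage. Under saliva it adds an intake rule: "Participants were asked not to ingest any type of food or drink with sugars, alcohol and/or caffeine, as well as tobacco, at least 12 hours" before testing.

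The Design section adds fasting ("All participants performed a series of tests, before which they had to fast") and repeatability ("The order and schedule (8 am) of the tests was the same for the 'final-test' and the same materials and procedures were used"). It describes two test days 30 days apart, and no screening or familiarisation draw. It also supplies a concurrent control: "This investigation was a triple blinded, randomized, placebo-controlled pilot study".

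The analytes include "Catecholamines such as dopamine, epinephrine and norepinephrine", together with serotonin, cortisol, CRH and ACTH. Whether cortisol was measured in blood or saliva is not stated.

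The SAP uses a two-way repeated ANOVA, without naming the two factors, followed by paired and unpaired t-tests to judge the effect of the intervention.

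**The concern.** The stress hormones are one of the main laboratory domains, and the documents themselves group several of them as such. The sampling text gives a minimum time for holding the saliva swab, yet says nothing about the participant's state before venepuncture: no seated or supine rest, no posture, no interval from arrival to needle. Repeating the same procedures at the second visit does not settle this, because an unspecified rest may vary from person to person, and because a second visit is more familiar than a first whatever the procedure.

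Two things follow if arousal just before the draw affects these analytes. That premise is general physiology; the documents do not quantify it.

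- Variation in arousal adds noise to both readings and lowers precision for every affected hormone.
- If arousal is on average higher at baseline, levels fall at the second visit with no supplement effect. If it is higher in one population than in the other, athletes and sedentary participants appear to respond differently.

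The Results contain patterns of this shape. In sedentary participants CRH is described as "decreasing significantly" on the synbiotic, and it fell on placebo too. Epinephrine fell in sedentary participants on the synbiotic. The athlete–sedentary difference in CRH (p<0.05) is presented as a different response to the synbiotic.

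**Working it through.** **Inputs.** From the documents: two draws, a randomised placebo control, paired and unpaired t-tests, and significance at 0.05 (sidedness not stated; two-sided taken here). Not in the documents: sample size, SDs, hormone values, power. There is therefore no stated figure to reproduce, and everything below is illustration on assumed inputs.

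**1. Where a visit effect goes.** Write the mean change in population p as v_p on placebo and v_p + τ_p on synbiotic, where v_p is the visit effect and τ_p the supplement effect.

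- Paired test in the synbiotic arm estimates v_p + τ_p.
- Synbiotic minus placebo within a population estimates τ_p.
- Athlete minus sedentary, synbiotic arms only, estimates (v_A − v_S) + (τ_A − τ_S).
- Difference of the two synbiotic-minus-placebo contrasts estimates τ_A − τ_S.

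Only the second and fourth are free of v. The first and third carry it in full.

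**2. Size for the tests that carry it.** Assume τ = 0, a visit-2 fall of δ = 0.3, 0.5 or 0.8 SD of the within-person change, and n = 6, 10 or 15 per arm.

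- Paired test: noncentral t, n − 1 df, noncentrality δ√n. Example: 0.5 × √10 = 1.58, giving 0.293.
- Athlete versus sedentary, synbiotic arms only, fall in sedentary participants alone: noncentral t, 2n − 2 df, noncentrality δ√(n/2). Example: 0.5 × √5 = 1.12, giving 0.185.
- Synbiotic significant while placebo is not, with the same fall in both arms: 50,000 simulated trials.

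Probability of a false significant result (nominal 0.05):

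| Fall (SD) | n per arm | Paired, one arm | Synbiotic significant, placebo not | Athlete vs sedentary, synbiotic arms only |
|---|---|---|---|---|
| 0.3 | 6 | 0.093 | 0.086 | 0.076 |
| 0.3 | 10 | 0.136 | 0.118 | 0.097 |
| 0.3 | 15 | 0.192 | 0.157 | 0.125 |
| 0.5 | 6 | 0.171 | 0.140 | 0.123 |
| 0.5 | 10 | 0.293 | 0.204 | 0.185 |
| 0.5 | 15 | 0.438 | 0.248 | 0.262 |
| 0.8 | 6 | 0.356 | 0.227 | 0.241 |
| 0.8 | 10 | 0.616 | 0.234 | 0.395 |
| 0.8 | 15 | 0.821 | 0.148 | 0.562 |

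In the same simulations the synbiotic-versus-placebo test on change rejects in about 5% of trials at every fall and n.

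To give the SD units a meaning: with an assumed SD of log change of 0.4, baseline excesses of 10%, 20% and 30% are ln(1.1)/0.4 = 0.24, ln(1.2)/0.4 = 0.46 and ln(1.3)/0.4 = 0.66 SD. At 12 per arm the paired test then rejects in 12%, 30% and 54% of trials.

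**3. Noise.** Suppose uncontrolled conditions raise the variance of change by 25%, 50% or 100%. The SD rises by √1.25 = 1.12, √1.5 = 1.22 or √2 = 1.41 times. For an assumed effect of 1 original SD, n per arm for 80% power is 2(1.96 + 0.84)² × the variance ratio, rounded up: 16 with no added noise, then 20, 24 or 32. With 10 per arm, power (noncentral t) falls from 56% to 47%, 41% or 32%.

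**4. Against the reported results.** CRH falling in sedentary participants on both synbiotic and placebo is what a shared visit effect predicts. Norepinephrine, ACTH and cortisol showed no significant change, CRH rose slightly in athletes, and dopamine rose in athletes on synbiotic; none of these is the predicted fall.

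**The case against.** The best defence has four parts.

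- **Silence is not absence.** The text is short and does not say that participants were drawn without rest. A reader might infer that there was none, or that participants were new to venepuncture; the documents support neither. Baseline is only the first draw documented in the trial. This stands.
- **The trial is already standardised and controlled.** Fasting, a fixed hour, the same order and procedures, and a randomised placebo arm are all in place. A reader might infer that the synbiotic-versus-placebo comparisons are biased. They are not: a shared visit effect cancels there in expectation, and the cost is precision. This stands in full for that comparison, but not for the paired tests or the comparison between populations, which randomisation to supplement does not protect.
- **The authors already discount part of it.** The Results say that the sedentary epinephrine fall may be a placebo effect and note the CRH fall on placebo. This stands for those two falls. It does not cover the athlete–sedentary CRH difference, which is still presented as a differing response to the synbiotic, with the slight athlete rise said not to be a placebo effect.
- **Other explanations fit as well.** A reader might take the sedentary CRH fall as proof of needle or arrival stress. It is not: placebo response, regression to the mean and the end of the exam period or season fit equally, and most of the reactive analytes did not move. Nor do the documents say that sedentary participants were less used to testing. This stands.

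**Conclusion.** The concern holds as a gap in the described sampling procedure and as a limit on interpretation. It does not show that the randomised comparison is invalid.

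Pre-draw rest and posture are not described for analytes plausibly sensitive to both. The loss of precision is of unknown size. A visit-2 fall is possible and, if present, would mislead only the before–after tests, the reading of significance in one arm but not the other, and the non-randomised athlete–sedentary comparison. On the assumed inputs, a shared fall of 0.5 SD raises false significance in a one-arm paired test from 5% to between 17% and 44%, and the one-arm-only pattern from about 5% to between 14% and 25%. These figures rest on normal changes, equal arms of 6 to 15, no true supplement effect and an assumed fall; the documents give none of them.

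The result most exposed is the athlete–sedentary CRH difference, because CRH also fell on placebo in sedentary participants.

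**What to change.** **For the data already collected**

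1. Report the rest, posture and time from arrival to draw used at each visit, or state that they were not controlled, and list this as a limitation.
2. For CRH and epinephrine, base any synbiotic claim on the synbiotic-versus-placebo contrast of change within each population, with a confidence interval. For athletes versus sedentary, use the difference between those two contrasts.
3. Do not present within-arm falls, or the athlete–sedentary CRH difference on synbiotic, as effects of the supplement.

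This needs only re-analysis and a few sentences. The price is wider intervals for the population question: with equal arms, the difference of contrasts has variance 4σ²/n against 2σ²/n for a single contrast, so its standard error is √2 = 1.41 times larger. That is the honest precision for the question asked.

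**For any successor to this pilot**

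Add one line to the sampling procedure requiring the same seated rest (for example 20 minutes) in the same posture before each draw at both visits. The cost is about 20 minutes per participant per visit. This addresses noise, which the placebo contrast cannot remove. It does not make the second visit as new as the first, so the placebo-controlled contrast is still needed.

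### Recent exercise is neither standardised nor recorded before the two sampling visits, which can confound the non-randomised athlete-versus-sedentary marker comparisons

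*Combined protocol and SAP*

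**What the plan says.** The Design section sets both visits at the same hour and in the same sequence ("The order and schedule (8 am) of the tests was the same") and requires fasting ("All participants performed a series of tests, before which they had to fast"). The Blood and saliva sampling section repeats the hour for blood ("Blood samples were collected from the subjects at 8 am") and adds the intake rule, which applies for at least 12 hours before the tests: "Participants were asked not to ingest any type of food or drink with sugars, alcohol and/or caffeine, as well as tobacco".

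The only instruction that touches on activity is in Design: "Subjects were asked to maintain their regular lifestyle". Activity is measured by device, but not symmetrically around the two samples: "Accelerometers were distributed one week prior to the baseline test and the week after the final test". The intervention month is described as one of possible physical and mental stress in both groups, "being at the end of an examination period, as well as the end of the soccer season".

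The markers are dopamine, epinephrine, norepinephrine, serotonin, cortisol, CRH, ACTH, IL-1β, IL-10 and salivary IgA. The SAP specifies a two-way repeated ANOVA followed by paired and unpaired t-tests at p<0.05. It names no covariate and does not say which two factors enter the ANOVA.

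**The concern.** The plan treats these markers as sensitive enough to pre-test conditions to fix clock time, food, caffeine, alcohol and tobacco. It leaves open the one condition that most separates its two groups. A player who follows the instructions may have trained or played the day before one sample and rested before the other. A sedentary participant is much less likely to have done either.

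The stated purpose is to find out whether the supplement acts differently in soccer players and in sedentary people. Nobody is randomised to those two groups. If time since last exercise differs between the groups at a visit, or shifts between visits in one group only, an acute exercise effect is mixed with training status and can be read as a differing response.

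**Working it through.** **1. Conditions before each sample, side by side**

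| Condition | Baseline | Final | Source |
|---|---|---|---|
| Hour and order | fixed, 8 am | same | Design |
| Fasting | required | required | Design |
| Sugars, alcohol, caffeine, tobacco | barred for at least 12 h | same | Blood and saliva sampling |
| Training or match | no rule | no rule | no section |
| Time since last exercise recorded | no | no | no section |
| Accelerometer in the preceding week | yes | no (worn the week after) | Design |

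The device data could partly describe exercise before the baseline sample, but not before the final one.

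**2. The calendar.** Design gives 30 days between tests. Since 30 = 4 × 7 + 2, a final test exactly 30 days after baseline falls two weekdays later. If training follows a weekly cycle (an assumption; no training schedule is given), the two tests fall at different points in that cycle unless this is arranged otherwise.

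**3. Size of a possible bias (assumed inputs only).** Let f be the share of athletes sampled with a carry-over from recent exercise, and d that carry-over in SD units. Take the share in sedentary people as zero for simplicity. The documents give neither f nor d.

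- Athlete-sedentary difference at one visit: bias = f × d. For f from 0.25 to 1.0 and d from 0.2 to 0.5, this runs from 0.25 × 0.2 = 0.05 SD to 1.0 × 0.5 = 0.50 SD.
- Change from baseline in athletes, and its difference from the sedentary change: bias = (f_final − f_baseline) × d. With d = 0.5, shares of 70% then 30% give (0.30 − 0.70) × 0.5 = −0.20 SD. Reversing the shares gives +0.20 SD. Going from 100% to 0% gives −0.50 SD. With equal shares the bias is zero.

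**4. The randomised contrast.** Within athletes, the expected shift (f_final − f_baseline) × d is the same in both arms, so synbiotic minus placebo has expected bias 0. The same holds for the athlete-sedentary difference in that net contrast: 0 − 0 = 0. What remains is noise. At one visit the added variance is f(1 − f)d², which is largest at f = 0.5. With d = 0.5 that is 0.25 × 0.25 = 0.0625 of the marker's variance.

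**5. Which comparisons are reported.** The Results section draws on comparisons that step 4 does not protect:

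- baseline contrasts, with serotonin higher in athletes and CRH apparently lower;
- within-group changes from baseline;
- a differing CRH response between athletes and sedentary people (p<0.05), although the sedentary fall also occurred on placebo. This suggests, without proving it, that the test was not net of the placebo change.

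The Results also credit training with the differing dopamine response.

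**The case against.** The strongest reply is the placebo arm. The question concerns the effect of the synbiotic in a randomised, placebo-controlled study, and any training-schedule effect falls on both athlete arms. That stands. A reader might infer that the gap biases the estimated supplement effect in athletes, and step 4 shows that it should not. The protection covers only contrasts taken net of placebo. The SAP does not commit to these, and the Results do not consistently use them.

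Second, the reported results fit an athlete-only artefact poorly. Cortisol, ACTH, norepinephrine and salivary IgA show no significant change. The significant IL-1β and CRH changes are in the sedentary group. The athletes' dopamine rise is said not to be a placebo effect, whereas a shared training artefact should also appear in placebo athletes. This stands as a reason not to claim that the gap explains any particular finding. Non-significance in a pilot does not show that there was no bias.

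Third, several tempting details have no support. Nothing shows that players rested more before the final test; the end of the season suggests that load may change, not in which direction. No rule prevents sedentary people from exercising. With a fasted 8 am sample, the likely exposure is the previous day or evening. Whether a given marker is still shifted by then cannot be established from the documents.

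Fourth, habitual training is the characteristic under study and keeping the regular lifestyle is a deliberate choice, so a long training ban would interfere with the design. That also stands and limits the fix.

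**Conclusion.** The concern holds in a limited form. Recent exercise is unstandardised and unrecorded, its likelihood differs between the two groups, and it may differ between visits. It can therefore confound the non-randomised athlete-sedentary marker comparisons, at baseline and in change, and the uncontrolled before-after changes in athletes. The within-athlete synbiotic-placebo contrast is affected mainly by noise, provided that both arms follow the same training and test schedule.

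The size is unknown. The figures of 0.05 to 0.50 SD at one visit and 0.20 SD in change are illustrations that rest on assumed shares and an assumed carry-over. The documents do not support the stronger reading that the reported hormone or cytokine findings are artefacts of recent exercise. This is a low-cost improvement to the design and a limit on interpretation; it does not invalidate the randomised comparison.

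**What to change.** Add to the pre-test rules, for all participants and both visits:

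- **One common exercise condition.** At minimum, no training or match within the existing 12-hour window, that is, from 8 pm the evening before an 8 am sample. Earlier exercise on the previous day remains possible, so the next two items are needed as well.
- **Matched timing.** Agree with the club that both tests fall at the same point in the training cycle, defined by time since the last session or match. Matching on weekday is not possible with exactly 30 days between tests.
- **A record.** Note hours since last exercise, and its type, at each test.

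In the SAP, use the recorded time at each visit as a covariate in a sensitivity analysis of the athlete-sedentary comparisons. If the two groups hardly overlap on it, the adjusted result depends on the model and should be read with that caution. The randomised contrast can stay unadjusted, since exercise before the final test follows randomisation.

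Because the document already reports results, state whether exercise before each sample was controlled, and report time since last training or match if it is known. If it was not recorded, list this as a limitation and restrict the statements that training altered the marker response.

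The cost is some scheduling with the club and one more recorded item. No 24 to 48 hour ban is needed, nor any rescheduling that would disturb the 30-day interval.
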